3.0 Introduction

This statistical analysis plan (SAP) describes the statistical analyses to be completed by the Data and Statistical Science Department for upadacitinib Study M15-557. It provides details to further elaborate statistical methods as outlined in the protocol.

Pharmacokinetic and biomarker analyses will be performed separately, and the corresponding analysis plan is documented separately.

Unless noted otherwise, all analyses will be performed using SAS version 9.2 or later (SAS Institute Inc., Cary, NC 27513) under the UNIX operating system.

4.0 Study Objectives, Design and Procedures

4.1 Study Objectives

Period 1

1. To compare the efficacy of upadacitinib 15 mg QD versus placebo for the treatment of signs and symptoms of subjects with moderately to severely active RA who are on a stable dose of csDMARDs and have an inadequate response to csDMARDs.
2. To compare the safety and tolerability of upadacitinib 15 mg QD versus placebo in subjects with moderately to severely active RA who are on a stable dose of csDMARDs and have an inadequate response to csDMARDs.

Period 2

To evaluate the long-term safety, tolerability, and efficacy of upadacitinib 15 mg QD in subjects with RA who have completed Period 1.

4.2 Overall Study Design and Plan

This is a Phase 3 multicenter study that includes two periods. Period 1 is a 12-week, randomized, double-blind, parallel-group, placebo-controlled period designed to compare

the safety and efficacy of upadacitinib 15 mg QD versus placebo for the treatment of signs and symptoms of subjects with moderately to severely active RA from China, Brazil, and South Korea who are on a stable dose of csDMARDs and have an inadequate response to csDMARDs. Period 2 is an open-label 52-week extension period to evaluate the long-term safety, tolerability, and efficacy of upadacitinib 15 mg QD in subjects from China, Brazil, and South Korea who have completed Period 1.

The study is designed to enroll approximately 322 subjects at approximately 50 study centers in China, Brazil and South Korea to meet scientific and regulatory objectives without enrolling an undue number of subjects in alignment with ethical considerations. Therefore, if the target number of subjects has been enrolled, there is a possibility that additional subjects in screening will not be enrolled.

The study duration will include a 35-day screening period; a 12-week randomized, double-blind, parallel-group, placebo-controlled treatment period (Period 1); an open-label 52-week extension period (Period 2); and a 30-day follow-up period (visit or call).

Subjects who meet eligibility criteria will be randomized in a 1:1 ratio to one of two treatment groups. It is expected that approximately 222 subjects will enter the study from China and 100 subjects from other countries including Brazil and South Korea:

- Group 1: upadacitinib 15 mg QD (Period 1) → upadacitinib 15 mg QD (Period 2)
- Group 2: Placebo (Period 1) → upadacitinib 15 mg QD (Period 2)

Randomization will be stratified by country.

Subjects must have been on a stable dose of csDMARD(s) for ≥ 4 weeks prior to the first dose of study drug and must remain on a stable dose until Week 24; the csDMARD dose may be decreased only for safety reasons. At Week 24, if a subject fails to meet the Low Disease Activity (LDA) criterion (LDA defined as CDAI ≤ 10) the investigator should adjust the subject's background RA therapies. Starting at Week 24 (after Week 24

assessments have been performed), initiation of or change in corticosteroids, non-steroidal anti-inflammatory drugs (NSAIDs), acetaminophen, low potency analgesics, or csDMARDs (restricted to oral or parenteral MTX, sulfasalazine, hydroxychloroquine, chloroquine and leflunomide, and restricted to concomitant use of up to 2 csDMARDs except the combination of MTX and leflunomide) is allowed as per local label. Starting at Week 24, at least 20% improvement in BOTH TJC AND SJC is required to remain in the study. Anyone who does not fulfill this criterion at 2 consecutive visits (starting at Week 24) must be discontinued from the study.

[figure not shown]
Subjects taking MTX should take oral folic acid throughout study participation. Folic acid dosing and timing of regimen will be based on the Investigator's discretion.

Subjects who complete the Week 12 visit (end of Period 1) will enter the open-label 52-week extension portion of the study, Period 2. Subjects who are assigned to upadacitinib treatment in Period 1 will continue to receive upadacitinib per original randomization assignment in an open-label manner. Subjects who are assigned to placebo in Period 1 will be switched to receive open-label upadacitinib from Week 12 onwards.

The primary analysis will be conducted after all subjects have completed Period 1 (Week 12) or have prematurely discontinued prior to Week 12.

Schematics of Period 1 and Period 2 are shown in [Figure 1](#).

Figure 1. **Study Design**

4.3 Sample Size

The planned total sample size of 322 for this study provides over 90% power for a 21.7% difference in ACR20 response rate at Week 12 (assuming a placebo ACR20 response rate of 36.7%), at two-sided significance level of 0.05 and accounting for a 10% dropout rate. This sample size will also provide at least 90% power for most of the key secondary endpoints, including change from baseline in DAS28 (CRP), ACR50 response rate, LDA and CR based on DAS28 (CRP), and SF-36 PCS, at two-sided significance level of 0.05 and accounting for a 10% dropout rate.

4.4 Interim Analysis and Data Base Lock

An unblinded analysis will be conducted after all subjects have completed Period 1 (Week 12) or have prematurely discontinued prior to Week 12 for the purpose of regulatory submission.

4.5 Data Monitoring Committee (DMC) Activities

An independent external Data Monitoring Committee (DMC) is used to review unblinded safety data at regular intervals during the conduct of the study. The DMC will provide recommendation to an AbbVie Point of Contact on whether to continue, modify, or terminate studies after each review. When needed, high level unblinded efficacy data may also be requested by the DMC and be reviewed so that the DMC can assess the benefit:risk of any emerging safety differences.

5.0 Analysis Populations and Analysis Windows

5.1 Analysis Populations

Full Analysis Set (FAS)

The Full Analysis Set (FAS) includes all randomized subjects who received at least one dose of study drug. The FAS will be used for all efficacy and baseline analyses.

Per Protocol Analysis Set

The Per Protocol Analysis Set represents a subset of the FAS and consists of all FAS subjects who did not meet any major protocol deviations during Period 1 of the study. Additional analysis of the primary efficacy endpoint will be conducted on the Per Protocol analysis set, in order to evaluate the impact of major protocol deviations.

Major protocol deviations (ICH deviations and other clinically significant non-ICH deviations) will be identified prior to database lock.

Safety Analysis Set

The Safety Analysis Set consists of all subjects who received at least one dose of study drug. For the Safety Analysis Set, subjects are assigned to a treatment group based on the "as treated" treatment group, regardless of the treatment randomized. The "as treated" is determined by the treatment the subject received during the majority of the subject's drug exposure time in the analysis period.

5.2 Analysis Windows

Definition of Study Days (Days Relative to the First Dose of Study Drug)

Study Days are calculated for each collection date relative to the date of the first dose of study drug. It is defined as the number of days between the date of the first dose of study drug and the collection date. Study days are negative values when the collection date of interest is prior to the first study drug dose date. Study days are positive values when the collection date of interest is on or after the first study drug dose date. The day of the first dose of study drug is defined as Study Day 1, while the day prior to the first study drug dose is defined as Study Day –1 (there is no Study Day 0). Study days are used to map actual study visits to the protocol-specified study visits.

Definition of Analysis Windows

The following rules will be applied to assign actual subject visits to protocol-specified visits. For each protocol-specified study visit, a target study day will be identified to represent the corresponding visit along with a window around the target day. Windows will be selected in a non-overlapping fashion so that a collection date does not fall into multiple visit windows. If a subject has two or more actual visits in one visit window, the visit closest to the target day will be used for analysis. If two visits are equidistant from the target day, then the later visit will be used for analysis.

The visit window and the target study day for each protocol-specified visit in Period 1 are displayed in [Table 1](#), [Table 2](#), [Table 3](#), [Table 4](#), and [Table 5](#) (depending on the different

visit schedules of different endpoints). Visit windows for protocol-specified visits in Period 2 are defined similarly.

Table 1. Analysis Windows for Efficacy Analysis for Period 1 (for ACR Components and Morning Stiffness)

Protocol Specified Visit Week	Lower Bound	Target Day	Upper Bound
Baseline	-99	1 ^a	1
1	2	8	11
2	12	15	22
4	23	29	43
8	44	57	71
12	72	85	min (99, first dose date of Period 2)

a. Day of first dose of study drug.

Table 2. Analysis Windows for Safety Analysis of Labs and Vital Signs for Period 1

Protocol Specified Visit Week	Lower Bound	Target Day	Upper Bound
Baseline	-99	1 ^a	1
2	2	15	22
4	23	29	43
8	44	57	71
12	72	85	min (99, first dose date of Period 2)

a. Day of first dose of study drug.

Table 3. Analysis Windows for Efficacy Analysis for Period 1 (for EQ-5D-5L, SF-36, FACIT-F and RA-WIS)

Protocol Specified Visit Week	Lower Bound	Target Day	Upper Bound
Baseline	-99	1 ^a	1
4	2	29	57
12	58	85	min (127, first dose date of Period 2)

a. Day of first dose of study drug.

Table 4. Analysis Windows for Safety Analysis of Lab Parameters IgG and IgM for Period 1

Protocol Specified Visit Week	Lower Bound	Target Day	Upper Bound
Baseline	-99	1 ^a	1
8	2	57	Min (99, first dose date of Period 2)

a. Day of first dose of study drug.

Table 5. Analysis Windows for Safety Analysis of Lymphocyte subsets Lab Parameters for Period 1

Protocol Specified Visit Week	Lower Bound	Target Day	Upper Bound
Baseline	-99	1 ^a	1
8	2	57	71
12	72	85	min (99, first dose date of Period 2)

a. Day of first dose of study drug.

6.0 Demographics, Baseline Characteristics, Medical History, and Previous/Concomitant Medications

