### **Follow-Up Period**

A Follow-Up Visit will occur approximately 30 days after the last dose of study drug to obtain information on any new or ongoing AE/SAEs, and to collect vital signs and clinical laboratory tests.

Subjects will complete the 30 day-Follow-Up Visit when they have either:

- Completed the last visit of Period 1 (Week 12), but decided not to participate in Period 2; OR
- Completed the last visit of Period 2; OR
- Prematurely discontinued study drug. If a PD visit has already occurred, then the 30 day Follow-Up visit may be a telephone call if a site visit is not possible.

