9.1.2 Definition of Missing Data Imputation

Non-Responder Imputation (NRI) Approach

The NRI approach will categorize any subject who has missing value for categorical variables at a specific visit as non-responder for that visit. In addition, subjects who prematurely discontinue from study drug will be considered as non-responders for all subsequent visits after discontinuation.

Observed Cases (OC)

The OC analysis will not impute values for missing evaluations, and thus a subject who does not have an evaluation on a scheduled visit will be excluded from the OC analysis for that visit. In addition, the OC will not use values after premature discontinuation of study drug. This sensitivity analysis will only be applied to the analysis in Period 1.

As Observed (AO)

The AO analysis will not impute values for missing evaluations, and thus a subject who does not have an evaluation on a scheduled visit will be excluded from the AO analysis for that visit. Regardless of treatment switching or premature discontinuation of study drug, all observed data will be used in the analysis. The AO analysis will be applied to long-term efficacy analysis.

Mixed Effect Model Repeat Measurement (MMRM)

The repeated measure analysis will be conducted using mixed model including observed measurements at all visits. The mixed model includes the categorical fixed effects of treatment, visit and treatment-by-visit interaction, main stratification factors at randomization, and the continuous fixed covariates of baseline measurement. An unstructured variance covariance matrix will be used. The parameter estimations are based on the assumption of data being missing at random and using the method of restrictive maximum likelihood (REML). The missing at random assumption is considered reasonable given the high placebo response rate typically seen in RA trials. Additionally, in RA trials, the proportion of discontinuation is relatively small (10 – 15% only) and the rate of discontinuation due to lack of efficacy is generally low (< 5%).

Multiple Imputation (MI)

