10.3 Analysis of Laboratory Data**10.3.1 Variables and Units**

All laboratory parameters to be collected in this study are listed below. Laboratory parameters will be reported using the standard international (SI) units.

Table 12. List of Laboratory Variables

Laboratory Variables
Hematology
White Blood Cell (WBC) Count
Red Blood Cell (RBC) Count
Hemoglobin
Hematocrit
Platelets count
Neutrophils
Basophils
Eosinophils
Lymphocytes
Monocytes
Bands
Chemistry
Total Bilirubin
Alkaline Phosphatase (ALP)
Serum glutamic oxaloacetic transaminase (SGOT/AST)
Serum glutamic pyruvic transaminase (SGPT/ALT)
Total Protein
Albumin
Glucose
Triglycerides
Blood Urea Nitrogen (BUN)
Creatinine
Uric acid
Sodium
Potassium
Calcium
Inorganic Phosphorus
Creatine Phosphokinase (CPK)
Chloride

Table 12. List of Laboratory Variables (Continued)

Laboratory Variables
Chemistry (continued)
Bicarbonate
Cholesterol
LDL cholesterol
HDL cholesterol
International Normalized Ratio (INR) reflex only
Urinalysis
Specific Gravity
pH
Protein
Glucose
Ketones
Blood
Microscopic Examination (if needed)
Urobilinogen
Bilirubin
Leukocytes
Nitrites
Other
hs-CRP
QuantiFERON-TB Gold ^a
IgG and IgM
ESR

a. For annual follow-up, QFT is captured only for those with negative QFT at Screening.

10.3.2 Analysis of Laboratory Data for Period 1

The laboratory data will be summarized by the "as treated" treatment groups (upadacitinib 15 mg QD and the placebo group).

10.3.2.1 Assessment of Mean Change from Baseline and Percent Change from Baseline in Clinical Laboratory Variables

Analyses of mean change from baseline in continuous hematology, chemistry, and urinalysis variables which are measured longitudinally will be performed by visits and by "as treated" treatment group. For each change from baseline analysis, the following summary statistics will be presented for each treatment group: sample size, baseline mean, visit mean, and the mean, standard deviation, and median of the changes from baseline. An ANOVA model with treatment as a factor will be used to test statistical significance for the change from baseline mean among different treatment groups.

In addition, similar analyses will be conducted for percentage change from baseline in hemoglobin, LDL-C, HDL-C, triglycerides, total cholesterol (TC), TC/HDL and LDL/HDL.

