10.3.2.2 Assessment of Shift from Baseline in Clinical Laboratory Variables

The baseline and post-baseline laboratory observations will be categorized as Grade 1, Grade 2, Grade 3, and Grade 4 according to OMERACT criteria (Rheumatology Common Toxicity Criteria v.2.0). For creatine phosphokinase and creatinine NCI CTC criteria will be used.

For each laboratory variable, shift tables will be generated that cross tabulate the subjects as deemed appropriate by "as treated" treatment group:

- Category of the baseline value versus category of the final value.
- Category of the baseline value versus maximum category.
- Category of the baseline value versus minimum category.

Note that the minimum/maximum category is used, rather than the category of the minimum/maximum value. The two may be different due to variation in the reference range.

No statistical tests will be performed for this analysis.

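### Period 1 laboratory and vital-sign values are windowed by study day alone, so a 30-day follow-up value from an early stopper is reported as a Week 4, 8 or 12 result

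*SAP*

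**What the plan says.** SAP 5.2 counts study days from the first dose and states that "Study days are used to map actual study visits to the protocol-specified study visits". Table 2, headed "Analysis Windows for Safety Analysis of Labs and Vital Signs for Period 1", gives Week 2 as Days 2-22, Week 4 as Days 23-43, Week 8 as Days 44-71, and Week 12 as Day 72 to the earlier of Day 99 and the first Period 2 dose. When two visits share a window, "the visit closest to the target day will be used for analysis", and the later one is taken if they tie. Period 2 windows are not tabulated; they are said to be defined in a similar way.

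Protocol 5.1 (Follow-Up Period) places a visit about 30 days after the last dose, to check adverse events "and to collect vital signs and clinical laboratory tests". It applies to subjects who stop study drug prematurely, with a telephone call allowed if a PD visit has taken place and a site visit is not possible.

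SAP 10.3.2.1 then says: "Analyses of mean change from baseline in continuous hematology, chemistry, and urinalysis variables which are measured longitudinally will be performed by visits", and adds an ANOVA between arms. SAP 10.4.2 summarises vital signs by visit in the same way, without a test. SAP 10.3.2.2 includes a shift table of "Category of the baseline value versus category of the final value".

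**The concern.** Nothing in Table 2 refers to the last dose. The Period 2 limit on Week 12 never applies to a subject who stops in Period 1, which leaves only Day 99. A follow-up value taken a month off drug therefore falls into whichever window its study day reaches and is summarised under that week's label in the subject's treatment group.

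The SAP sets a cut-off for other data. For efficacy, "the OC will not use values after premature discontinuation of study drug"; the MMRM in Appendix C excludes the same data; NRI scores it as non-response. Adverse events count up to 30 days after last dose (SAP 10.2). SAP 10.1, 10.3.2 and 10.4.2 and protocol 8.1.5.3 contain no such limit for Period 1 laboratory and vital-sign values. The nearest wording, in SAP 10.3.3.2, concerns long-term potentially clinically significant values, not the by-visit summaries.

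At stake is what a Week 8 or Week 12 upadacitinib mean describes. Early stoppers include subjects taken off drug for laboratory abnormalities under protocol Table 8. If their values recover off drug, the by-visit means and ANOVA understate the drug's effect.

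**Working it through.** **Inputs.** Windows and tie rule: SAP Table 2 and 5.2. Follow-up at last dose + 30 days: protocol 5.1. PD visit preferably within 14 days of stopping: protocol 5.1. Arm size 161: 322 / 2. Dropout 10%: SAP 4.3. Discontinuation 10-15%: SAP 9.1.2. Assumed, because the documents do not say: stopping days uniform over Days 1-84, PD visit 1-14 days after last dose, follow-up at 30 ± 3 days, and every stopper attending on site.

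SAP 4.3 supplies the arm size and dropout rate. Its power statement reproduces: 161 × 0.9 ≈ 145 per arm, 36.7% against 58.4%, two-sided 0.05, gives 96.3%, which is over 90%. Nothing below depends on it.

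**Step 1: where the follow-up lands.** Follow-up day = last-dose day + 30.

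| Last dose | Follow-up | Window | Stopping days (of 84) |
|---|---|---|---|
| Days 1-13 | Days 31-43 | Week 4 | 13 |
| Days 14-41 | Days 44-71 | Week 8 | 28 |
| Days 42-69 | Days 72-99 | Week 12 | 28 |
| Days 70-84 | Days 100-114 | none | 15 |

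Moving the follow-up by 3 days shifts these boundaries by 3 days.

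**Step 2: competition with an on-drug value.** The widest windows run 28 days (44-71 and 72-99), so two values in one window are at most 27 days apart. At 30 days after last dose the follow-up never shares a window with a value taken on or before the last dose. At 27 days it can share one in two cases (last dose on Day 44 or Day 72). The on-drug value is then 13 days from target and the follow-up 14, so the on-drug value is kept. Over all stopping days 1-84 and offsets of 27-33 days, no on-drug value is displaced.

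**Step 3: competition with a PD value.** This can go either way.
- Last dose Day 58, PD Day 72, follow-up Day 88: distances from Day 85 are 13 and 3, so the follow-up is used.
- Last dose Day 68, PD Day 72, follow-up Day 98: both are 13 days away, so the later value, the follow-up, is used.
- Of the 69 stopping days in Step 1 that reach a window, the follow-up is used for all 69 if the PD visit is 0-1 day after last dose, 63 if 7 days, and 52 if 14 days.

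Simulating 400,000 stoppers under the assumptions above, the follow-up value is used in some window for 73% and in the Week 12 window for 29.6%. It displaces a PD value in about 6%.

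**Step 4: size at Week 12.**
- 10% stopping: 161 × 0.10 = 16.1 stoppers per arm; 16.1 × 0.296 = 4.8.
- 15% stopping: 161 × 0.15 = 24.2; 24.2 × 0.296 = 7.1 to 7.2.
- Share of Week 12 values, taking as denominator completers + stoppers on Days 70-84 + affected: 4.8 / (144.9 + 2.9 + 4.8) = 3.1%; 7.2 / (136.9 + 4.3 + 7.2) = 4.8%.
- Ignoring PD visits altogether: 16.1 × 28/84 = 5.4 and 24.2 × 28/84 ≈ 8.0 per arm.
- At 50% attendance: 4.8 × 0.5 = 2.4 and 7.2 × 0.5 = 3.6 per arm.

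**The case against.** The strongest reply is that using every collected value is a legitimate safety convention. The summaries are labelled by visit and as-treated group, not as on-treatment, and the SAP already counts adverse events to 30 days after last dose. Because the follow-up value nearly always fills an empty window, the alternative is usually no value rather than an on-drug value. Excluding it leaves later means based on subjects who tolerated the drug, which can also hide an effect.

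Much of this stands. Neither option is free of selection, and no direction of bias can be shown from the documents; dilution depends on recovery off drug. But a 30-day tail suits incidence counts. It does not justify calling a value a month off drug a Week 8 or Week 12 result, and a separate follow-up row keeps the data without that label.

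The size is also open to challenge. Protocol 5.1 (Premature Discontinuation) makes the 30-day contact depend on the subject's willingness, although the Follow-Up Period text is firmer, and a telephone call yields no values. Attendance is unknown, so the full-attendance count is an upper figure.

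A reader might infer that off-drug values push out on-drug ones. Step 2 shows they do not. A reader might also infer that safety signals are lost. Worst-category shifts, Grade 3/4 counts and liver elevations use post-baseline extremes and cannot lose an on-drug abnormality this way.

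**Conclusion.** The point holds for the Period 1 by-visit laboratory and vital-sign means and the between-arm laboratory ANOVA. As written, the rule places a value from about 30 days after last dose in the Week 4, 8 or 12 window for any subject whose last dose is on Days 1-69 and who attends follow-up, unless a PD value in the same window is closer to target. Later stoppers and Period 1 completers are unaffected.

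With full on-site attendance and uniform stopping days, about 5-7 subjects per arm (3-5% of values) are affected at Week 12; at 50% attendance, about 2-4. Some dilution is likely for parameters that recover off drug. The primary endpoint is untouched. This should be corrected, but it does not threaten the trial's main conclusions.

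Two extensions are conditional. It is tempting to say that the baseline-to-final shift table is affected for every early stopper, but the SAP does not define the final value. If it means the last windowed Period 1 value, stoppers from Day 70 on are not affected. It is also tempting to say that the same happens in Period 2. That holds only if the Period 2 windows, which are not shown, also lack a limit relative to last dose; no between-arm laboratory test is planned there.

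**What to change.** Add to SAP 5.2, for both periods: by-visit laboratory and vital-sign summaries, and the final value in the shift table, use only values within a stated number of days after the last dose in that period. The sponsor sets the number. It must be shorter than the follow-up interval; 14 days, the protocol's preferred limit for the PD visit, is one option, though it still admits PD values up to two weeks off drug. Report the 30-day follow-up visit as its own row, and keep all values in the listings and in the worst-grade and potentially clinically significant counts.

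The cost is a short SAP addition, one programming condition and one extra table row. Slightly fewer values enter the by-visit means, which then describe only subjects on drug or recently off it. A table footnote should say so.

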### **Period 1 (12-Week Randomized, Double-Blind Treatment Period)**

Period 1 will begin at the Baseline Visit (Day 1) and will end at the Week 12 Visit. At the Baseline Visit, subjects who meet all the inclusion criteria and none of the exclusion criteria described in Section 5.2.1 and Section 5.2.2 will be enrolled into the study and randomized to double-blind treatment. During this period of the study, subjects will visit the study site at Weeks 1, 2, 4, 8, and 12. A  $\pm$  3 day window is permitted around scheduled study visits. The study drug dose taken the day prior to the Week 12 visit is considered the last dose in Period 1. Subjects who complete Period 1, but decide not to continue in Period 2 should complete a 30 day follow-up visit after the last dose of study drug.

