### **5.3 Efficacy Pharmacokinetic, Pharmacodynamic, Exploratory Research and Validation Studies, and Safety Assessments/Variables**

#### **5.3.1 Efficacy and Safety Measurements Assessed and Flow Chart**

Study procedures described are listed in the following section of this protocol and are summarized in tabular format in [Table 3](#).

**Table 3.** Study Activities (Period 1)

Activity	Screening		BL	Wk 1	Wk 2	Wk 4	Wk 8	Wk 12/PPD a	30-Day F/U Visit c
	D -35 to D -1	D 1 b							
Informed Consent d	X d								
Inclusion/Exclusion Criteria	X	X							
Medical/Surgical History e	X	X							
Alcohol and Nicotine Use	X								
Adverse Event Assessment f	Only SAEs and protocol-related nonserious AEs	X	X	X	X	X	X	X	X
Prior/Concomitant Therapy	X	X	X	X	X	X	X	X	X
Patient Questionnaires g		X	X	X	X	X	X		
PtGA									
Pain (VAS)									
HAQ-DI									
Morning Stiffness (Severity and Duration)									
Patient Questionnaires g		X					X	X	
EQ-5D-5L									
SF-36									
FACIT-F									
RA-WIS									
Latent TB Risk Assessment Form h		X						X i	
Central Lab Quantiferon-TB Gold Test h (and/or Local PPD Skin Test)		X						X i	

**Table 3.** Study Activities (Period 1) (Continued)

Activity	Screening		BL	Wk 1	Wk 2	Wk 4	Wk 8	Wk 12/PD a	30-Day F/U Visit c
	D -35 to D -1	D 1 b							
Chest X-Ray j	X								
12-Lead ECG k	X							X k	
Height (Screening Only) and Weight	X	X		X	X	X	X	X	X
Vital Signs l	X	X	X	X	X	X	X	X	X
Physical Exam m	X	X	X				X		
Physician Global Assessment (PhGA)	X	X	X	X	X	X	X	X	X
TJC68/SJC66	X	X	X	X	X	X	X	X	X
Serum Pregnancy Test at Central Lab n	X								
Local Urine Pregnancy Test o	X			X	X	X	X	X	X
Central Lab Tests	X	X	X	X	X	X	X	X	X
hsCRP p									
Blood Chemistry q									
Hematology (CBC)									
Urinalysis r									
ESR (Local Lab)	X	X	X	X	X	X	X	X	X

**Table 3.** Study Activities (Period 1) (Continued)

Activity	Screening		BL	Wk 1	Wk 2	Wk 4	Wk 8	Wk 12/PD a	30-Day F/U Visit c
	D -35 to D -1	D 1 b							
Other Central Lab Tests	X								
Rheumatoid Factor									
Anti-CCP Autoantibodies									
HBV/HCV Screening s									
Syphilis Screening (in mainland China only)									

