- s. At Screening only. For mainland China only, subjects with HBs Ab+ and/or HBC Ab+ and negative HBV DNA at screening, HBV DNA PCR test should be performed every 12 weeks. HBV DNA PCR testing every 12 weeks is not necessary when the subject has a history of HBV vaccine and HBs Ab+.
- t. Subjects will be tested for antibodies to HIV at Screening. The results of the HIV Ab testing will be retained by the study site under confidential restriction.
- u. At Week 1 and Week 2 visits, PK samples should be collected prior to dosing and the subjects should take the study drug dose at the clinic after collecting the PK blood sample. However, if the subject normally takes the study drug dose at a time that is after the time of the scheduled study visit, the subject should follow the regular dosing schedule and the PK sample should be collected at any time during the visit.
- v. PK samples should be collected at any time during the visit. Subject should follow the regular dosing schedule.
- w. In Vivo Pharmacodynamic biomarkers will not be collected for subjects in mainland China.
- x. Samples only collected if subject provides written consent and if not prohibited by local regulations. Optional samples for Exploratory Research and Validation Studies will not be collected for subjects in mainland China.
- y. For subjects entering Period 2.
- Note: Visit window is  $\pm 3$  days for Period 1. Any of the procedures may be performed at an unscheduled visit at the discretion of the Investigator.

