### **Height and Weight**

Height will be measured at the Screening Visit only (with shoes off). Body weight will be measured at all scheduled visits except Week 1 as specified in [Table 3](#) and [Table 5](#). All measurements will be recorded in metric units where applicable.

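### SAP Table 2 has no Week 1 window for labs and vital signs, so scheduled Week 1 values are left out of the Period 1 by-visit safety summaries or reported as Week 2

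*SAP*

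**What the plan says.** **Collection.** Protocol 5.1 states that in Period 1 "subjects will visit the study site at Weeks 1, 2, 4, 8, and 12", each with a tolerance of 3 days either way. In Protocol Table 3 the vital signs row and the row headed "Central Lab Tests" (hsCRP, chemistry, hematology, urinalysis) are marked right across. Body weight is different: "Body weight will be measured at all scheduled visits except Week 1".

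**Windows.** SAP 5.2 undertakes to set a target day and a window for every visit in the protocol, with separate tables because endpoints follow different schedules. Table 1 (ACR components and morning stiffness) has Week 1 at Days 2 to 11, target 8, and Week 2 at Days 12 to 22, target 15. Table 2, titled "Analysis Windows for Safety Analysis of Labs and Vital Signs for Period 1", has rows for Baseline and Weeks 2, 4, 8 and 12 only. Its Week 2 row runs from Day 2 to Day 22, target 15. Within a window, "If a subject has two or more actual visits in one visit window, the visit closest to the target day will be used for analysis"; ties go to the later visit.

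**Use.** SAP 10.1, 10.3.2.1 and 10.4.2 plan mean change from baseline by visit for laboratory variables and vital signs in Period 1. For laboratory variables, 10.3.2.1 adds an ANOVA comparing the treatment groups.

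**The concern.** A visit at which safety data are scheduled has no place in the by-visit tables, and the SAP gives no reason. Differing endpoint schedules cannot be the reason, because labs and vital signs are scheduled at Week 1.

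Two things are at stake. The first on-treatment hematology, chemistry and blood pressure values drop out of the by-visit picture in the only placebo-controlled period of the study. And the column labelled Week 2 may hold a mixture: true Week 2 values for most subjects, and values from about a week earlier for those whose Week 2 sample is missing or late. Neutropenia, lymphopenia, lipid changes and CPK elevation are listed as events of special interest in Protocol 6.1.1.3, so the early time course of these parameters has some interest.

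**Working it through.** **Step 1. Are the data scheduled at Week 1?** In the machine-read text of Protocol Table 3 the columns do not line up with the visits, so position needs an anchor. The weight row is blank in its third cell, and the protocol text says weight is skipped at Week 1. That identifies the third cell as Week 1. The vital signs and central laboratory rows carry a mark there. Separately, ACR20 at Week 1 is a key secondary endpoint (Protocol 5.3.3.1.2) and hsCRP is an ACR component, and hsCRP is listed in the same laboratory block as chemistry and hematology.

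**Step 2. Reproduce Table 2.** Cut halfway between neighbouring target days (rounded down), start at Day 2, and end at Day 99. With targets 15, 29, 57 and 85:

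- (15 + 29)/2 = 22
- (29 + 57)/2 = 43
- (57 + 85)/2 = 71

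The windows are 2–22, 23–43, 44–71 and 72–99, which match Table 2 exactly (its last bound is also capped at the first Period 2 dose). Table 2 is what this rule gives if there is no Week 1 visit.

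**Step 3. Both visits on time.** Week 1 is Day 8 ± 3, that is Days 5 to 11. Week 2 is Day 15 ± 3, that is Days 12 to 18.

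- Distance of Week 1 from Day 15: 15 − 11 = 4 at the least, 15 − 5 = 10 at the most.
- Distance of Week 2 from Day 15: 0 to 3.

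Since 3 < 4, the Week 2 value is selected in all 7 × 7 = 49 combinations of days and the Week 1 value is not used.

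**Step 4. Week 2 value missing.** The Week 1 value is then the only scheduled one within Days 2 to 22 and is reported as Week 2. A Day 8 sample is 15 − 8 = 7 days before the target.

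**Step 5. Week 2 visit late (Days 19 to 22).** The Week 1 value is selected if it is strictly closer to Day 15. With Week 1 on Day 11 (distance 4) and Week 2 on Day 20 (distance 5), Day 11 is used. The pairs (Week 1 day, Week 2 day) for which this happens are (9, 22), (10, 21), (10, 22), (11, 20), (11, 21) and (11, 22). Extra samples can add to this, since the note to Protocol Table 3 says "Any of the procedures may be performed at an unscheduled visit at the discretion of the Investigator".

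**Step 6. Add Week 1.** With targets 8, 15, 29, 57 and 85, the new cut is (8 + 15)/2 = 11.5, so Week 1 is Days 2–11 and Week 2 is Days 12–22. Later weeks do not change. These are the Table 1 windows. All six pairs in Step 5 then resolve correctly, because a Day 9 to 11 value no longer competes with a Day 20 to 22 value.

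**The case against.** **The premise rests on a poorly extracted table.** As read, Table 3 has more columns than visits, and the weight row has six marks after its blank where only five visits remain. A fully marked row is weak proof by itself. Nor does it help that the protocol text names no Week 1 exception for vital signs: SF-36 is not collected at Week 1 either, and no sentence says so. Both points are fair. The premise stands on the weight anchor and the Week 1 hsCRP draw, and can be confirmed by looking at the table in the PDF.

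**The impact is easily overstated.** A reader might infer that early changes in neutrophils, lymphocytes, lipids or CPK cannot be seen at all. The documents do not support that. Shift tables use the maximum and minimum category (SAP 10.3.2.2), Grade 3 or 4 values with worsening are counted (10.3.2.3), and so are post-baseline liver elevations (10.3.2.4). None of these is stated to be limited to windowed values. Protocol 8.1.5.3 also plans change to minimum and maximum, and a data monitoring committee reviews unblinded safety data. Nor can one say that Week 1 values never reach the mean-change tables: Steps 4 and 5 show that some do, under the wrong label.

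**Choosing which visits to tabulate is a reporting decision, and the same window applies to both arms.** True: there is no built-in direction of bias. But a decision to leave out Week 1 should be stated, and it would not remove the mislabelling while the Week 2 window still starts at Day 2.

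**Conclusion.** The point holds as a gap in the by-visit safety summaries and goes no further. SAP Table 2 omits a visit at which the protocol schedules labs and vital signs other than weight. For weight, having no Week 1 window is right.

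Size: one of five scheduled post-baseline Period 1 visits (1/5 = 20%) is missing from these tables, at most 322 laboratory panels and vital-sign sets if every planned subject attends. That is a missing table column and not a loss from the safety assessment as a whole. How many Week 1 values would be shown as Week 2 cannot be calculated, since the documents give no rate of missed or late Week 2 samples.

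The primary endpoint and the ranked secondary endpoints are untouched. Week 1 hsCRP is kept for efficacy through Table 1. The conclusion assumes that Table 3 is read correctly at Week 1 and that the Table 2 windows are applied as written. The priority is low, but the correction is cheap.

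**What to change.** For laboratory tests, blood pressure, pulse, respiratory rate and temperature, replace the first post-baseline row of SAP Table 2 with the two rows already in Table 1:

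- Week 1: Days 2 to 11, target 8
- Week 2: Days 12 to 22, target 15

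Leave Weeks 4, 8 and 12 as they are. SAP 10.4.1 counts body weight as a vital sign, so keep the current Table 2 windows for weight in a footnote or a separate row.

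The cost is one more column in the by-visit safety tables and the weight footnote. If the sponsor prefers not to tabulate Week 1, the SAP should say so and why, and should still start the Week 2 window at Day 12 for these measures so that Week 1 values are not reported as Week 2.
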